## 11.0 ENDPOINT EVALUATION CRITERIA/MEASUREMENT OF EFFECT

---

### 11.1 Response Criteria

Response and progression will be evaluated in this study using the new international criteria proposed by the revised Response Evaluation Criteria in Solid Tumors (RECIST) guideline (version 1.1). [20] Changes in the largest diameter (unidimensional measurement) of the tumor lesions and the shortest diameter in the case of malignant lymph nodes are used in the RECIST criteria.

#### 11.1.1 Definitions

Evaluable for toxicity. All participants will be evaluable for toxicity from the time of their first treatment with FOLFIRI plus panitumumab.

Evaluable for objective response. Only those participants who have measurable disease present at baseline, have received at least one cycle of therapy, and have had their disease re-evaluated will be considered evaluable for response. These participants will have their response classified according to the definitions stated below.

Evaluable Non-Target Disease Response. Participants who have lesions present at baseline that are evaluable but do not meet the definitions of measurable disease, have received at least one cycle of therapy, and have had their disease re-evaluated will be considered evaluable for non-target disease. The response assessment is based on the presence, absence, or unequivocal progression of the lesions.

#### Disease Parameters

Measurable disease. Measurable lesions are defined as those that can be accurately measured in at least one dimension (longest diameter to be recorded) as  $\geq 20$  mm by chest x-ray or as  $\geq 10$  mm with CT scan, MRI, or calipers by clinical exam. All tumor measurements must be recorded in millimeters (or decimal fractions of centimeters).

Malignant lymph nodes. To be considered pathologically enlarged and measurable, a lymph node must be  $\geq 15$  mm in short axis when assessed by CT scan (CT scan slice thickness recommended to be no greater than 5 mm). At baseline and in follow-up, only the short axis will be measured and followed.

Non-measurable disease. All other lesions (or sites of disease), including small lesions (longest diameter  $< 10$  mm or pathological lymph nodes with  $\geq 10$  to  $< 15$  mm short axis), are considered non-measurable disease. Bone lesions, leptomeningeal disease, ascites, pleural/pericardial effusions, lymphangitis cutis/pulmonitis, inflammatory breast disease, and abdominal masses (not followed by CT or MRI), are considered as non-measurable.

Note: Cystic lesions that meet the criteria for radiographically defined simple cysts should not be considered as malignant lesions (neither measurable nor non-measurable) since they are, by definition, simple cysts.

'Cystic lesions' thought to represent cystic metastases can be considered as measurable lesions, if they meet the definition of measurability described above. However, if non-cystic lesions are present in the same participant, these are preferred for selection as target lesions.

Target lesions. All measurable lesions up to a maximum of 2 lesions per organ and 5 lesions in total, representative of all involved organs, should be identified as **target lesions** and recorded and measured at baseline. Target lesions should be selected on the basis of their size (lesions with the longest diameter), be representative of all involved organs, but in addition should be those that lend themselves to reproducible repeated measurements. It may be the case that, on occasion, the largest lesion does

not lend itself to reproducible measurement in which circumstance the next largest lesion which can be measured reproducibly should be selected. A sum of the diameters (longest for non-nodal lesions, short axis for nodal lesions) for all target lesions will be calculated and reported as the baseline sum diameters. If lymph nodes are to be included in the sum, then only the short axis is added into the sum. The baseline sum diameters will be used as reference to further characterize any objective tumor regression in the measurable dimension of the disease.

Non-target lesions. All other lesions (or sites of disease) including any measurable lesions over and above the 5 target lesions should be identified as **non-target lesions** and should also be recorded at baseline. Measurements of these lesions are not required, but the presence, absence, or in rare cases unequivocal progression of each should be noted throughout follow-up.

#### 11.1.2 Methods for Evaluation of Measurable Disease

All measurements should be taken and recorded in metric notation using a ruler or calipers. All baseline evaluations should be performed as closely as possible to the beginning of treatment and never more than 4 weeks before the beginning of the treatment.

The same method of assessment and the same technique should be used to characterize each identified and reported lesion at baseline and during follow-up. Imaging-based evaluation is preferred to evaluation by clinical examination unless the lesion(s) being followed cannot be imaged but are assessable by clinical exam.

Clinical lesions Clinical lesions will only be considered measurable when they are superficial (*e.g.*, skin nodules and palpable lymph nodes) and  $\geq 10$  mm diameter as assessed using calipers (*e.g.*, skin nodules). In the case of skin lesions, documentation by color photography, including a ruler to estimate the size of the lesion, is recommended.

Chest x-ray Lesions on chest x-ray are acceptable as measurable lesions when they are clearly defined and surrounded by aerated lung. However, CT is preferable.

Conventional CT and MRI This guideline has defined measurability of lesions on CT scan based on the assumption that CT slice thickness is 5 mm or less. If CT scans have slice thickness greater than 5 mm, the minimum size for a measurable lesion should be twice the slice thickness. MRI is also acceptable in certain situations (*e.g.* for body scans).

Use of MRI remains a complex issue. MRI has excellent contrast, spatial, and temporal resolution; however, there are many image acquisition variables involved in MRI, which greatly impact image quality, lesion conspicuity, and measurement. Furthermore, the availability of MRI is variable globally. As with CT, if an MRI is performed, the technical specifications of the scanning sequences used should be optimized for the evaluation of the type and site of disease. Furthermore, as with CT, the modality used at follow-up should be the same as was used at baseline and the lesions should be measured/assessed on the same pulse sequence. It is beyond the scope of the RECIST guidelines to prescribe specific MRI pulse sequence parameters for all scanners, body parts, and diseases. Ideally, the same type of scanner should be used and the image acquisition protocol should be followed as closely as possible to prior scans. Body scans should be performed with breath-hold scanning techniques, if possible.

PET-CT: At present, the low dose or attenuation correction CT portion of a combined PET-CT is not always of optimal diagnostic CT quality for use with RECIST measurements. However, if the site can document that the CT performed as part of a PET-CT is of identical diagnostic quality to a diagnostic CT (with IV and oral contrast), then the CT portion of the PET-CT can be used for RECIST measurements and can be used interchangeably with conventional CT in accurately measuring cancer lesions over time.

Note, however, that the PET portion of the CT introduces additional data which may bias an investigator if it is not routinely or serially performed.

Ultrasound: Ultrasound is not useful in assessment of lesion size and should not be used as a method of measurement. Ultrasound examinations cannot be reproduced in their entirety for independent review at a later date and, because they are operator dependent, it cannot be guaranteed that the same technique and measurements will be taken from one assessment to the next. If new lesions are identified by ultrasound in the course of the study, confirmation by CT or MRI is advised. If there is concern about radiation exposure at CT, MRI may be used instead of CT in selected instances.

Endoscopy, Laparoscopy: The utilization of these techniques for objective tumor evaluation is not advised. However, such techniques may be useful to confirm complete pathological response when biopsies are obtained or to determine relapse in trials where recurrence following complete response (CR) or surgical resection is an endpoint.

Tumor markers: Tumor markers alone cannot be used to assess response. If markers are initially above the upper normal limit, they must normalize for a participant to be considered in complete clinical response. Specific guidelines for both CA-125 response (in recurrent ovarian cancer) and PSA response (in recurrent prostate cancer) have been published [*JNCI* 96:487-488, 2004; *J Clin Oncol* 17, 3461-3467, 1999; *J Clin Oncol* 26:1148-1159, 2008]. In addition, the Gynecologic Cancer Intergroup has developed CA-125 progression criteria which are to be integrated with objective tumor assessment for use in first-line trials in ovarian cancer [*JNCI* 92:1534-1535, 2000].

Cytology, Histology: These techniques can be used to differentiate between partial responses (PR) and complete responses (CR) in rare cases (*e.g.*, residual lesions in tumor types, such as germ cell tumors, where known residual benign tumors can remain).

The cytological confirmation of the neoplastic origin of any effusion that appears or worsens during treatment when the measurable tumor has met criteria for response or stable disease is mandatory to differentiate between response or stable disease (an effusion may be a side effect of the treatment) and progressive disease.

FDG-PET While FDG-PET response assessments need additional study, it is sometimes reasonable to incorporate the use of FDG-PET scanning to complement CT scanning in assessment of progression (particularly possible 'new' disease). New lesions on the basis of FDG-PET imaging can be identified according to the following algorithm:

- a. Negative FDG-PET at baseline, with a positive FDG-PET at follow-up is a sign of PD based on a new lesion.
- b. No FDG-PET at baseline and a positive FDG-PET at follow-up: If the positive FDG-PET at follow-up corresponds to a new site of disease confirmed by CT, this is PD. If the positive FDG-PET at follow-up is not confirmed as a new site of disease on CT, additional follow-up CT scans are needed to determine if there is truly progression occurring at that site (if so, the date of PD will be the date of the initial abnormal FDG-PET scan). If the positive FDG-PET at follow-up corresponds to a pre-existing site of disease on CT that is not progressing on the basis of the anatomic images, this is not PD.
- c. FDG-PET may be used to upgrade a response to a CR in a manner similar to a biopsy in cases where a residual radiographic abnormality is thought to represent fibrosis or scarring. The use of FDG-PET in this circumstance should be prospectively described in the protocol and supported by disease-specific medical literature for the indication. However, it must be acknowledged that both approaches may lead to false positive CR due to limitations of FDG-PET and biopsy

resolution/sensitivity. Note: A 'positive' FDG-PET scan lesion means one which is FDG avid with an uptake greater than twice that of the surrounding tissue on the attenuation corrected image.

### 11.1.3 Response Criteria

#### 11.1.3.1 *Evaluation of Target Lesions*

Complete Response (CR): Disappearance of all target lesions. Any pathological lymph nodes (whether target or non-target) must have reduction in short axis to <10 mm.

Partial Response (PR): At least a 30% decrease in the sum of the diameters of target lesions, taking as reference the baseline sum diameters.

Progressive Disease (PD): At least a 20% increase in the sum of the diameters of target lesions, taking as reference the smallest sum on study (this includes the baseline sum if that is the smallest on study). In addition to the relative increase of 20%, the sum must also demonstrate an absolute increase of at least 5 mm. (Note: the appearance of one or more new lesions is also considered progressions).

Stable Disease (SD): Neither sufficient shrinkage to qualify for PR nor sufficient increase to qualify for PD, taking as reference the smallest sum diameters while on study.

#### 11.1.3.2 *Evaluation of Non-Target Lesions*

Complete Response (CR): Disappearance of all non-target lesions and normalization of tumor marker level. All lymph nodes must be non-pathological in size (<10 mm short axis).

Note: If tumor markers are initially above the upper normal limit, they must normalize for a participant to be considered in complete clinical response.

Non-CR/Non-PD: Persistence of one or more non-target lesion(s) and/or maintenance of tumor marker level above the normal limits.

Progressive Disease (PD): Appearance of one or more new lesions and/or *unequivocal progression* of existing non-target lesions. *Unequivocal progression* should not normally trump target lesion status. It must be representative of overall disease status change, not a single lesion increase.

Although a clear progression of "non-target" lesions only is exceptional, the opinion of the treating physician should prevail in such circumstances, and the progression status should be confirmed at a later time by the review panel (or Principal Investigator).

#### 11.1.4 Evaluation of Best Overall Response:

The best overall response is the best response recorded from the start of the treatment until disease progression/recurrence (taking as reference for progressive disease the smallest measurements recorded since the treatment started). The participant's best response assignment will depend on the achievement of both measurement and confirmation criteria.

#### **For Participants with Measurable Disease (*i.e.*, Target Disease)**

Target Lesions	Non-Target Lesions	New Lesions	Overall Response	Best Overall Response when Confirmation is Required*
CR	CR	No	CR	≥4 wks. Confirmation**
CR	Non-CR/Non-PD	No	PR	≥4 wks. Confirmation**
CR	Not evaluated	No	PR	
PR	Non-CR/Non-PD/not evaluated	No	PR	
SD	Non-CR/Non-PD/not evaluated	No	SD	Documented at least once ≥4 wks. from baseline**
PD	Any	Yes or No	PD	no prior SD, PR or CR

Any	PD***	Yes or No	PD
Any	Any	Yes	PD

\* See RECIST 1.1 manuscript for further details on what is evidence of a new lesion.  
\*\* Only for non-randomized trials with response as primary endpoint.  
\*\*\* In exceptional circumstances, unequivocal progression in non-target lesions may be accepted as disease progression.  
Note: Participants with a global deterioration of health status requiring discontinuation of treatment without objective evidence of disease progression at that time should be reported as “*symptomatic deterioration.*” Every effort should be made to document the objective progression even after discontinuation of treatment.

### For Participants with Non-Measurable Disease (*i.e.*, Non-Target Disease)

Non-Target Lesions	New Lesions	Overall Response
CR	No	CR
Non-CR/non-PD	No	Non-CR/non-PD*
Not all evaluated	No	not evaluated
Unequivocal PD	Yes or No	PD
Any	Yes	PD

\* ‘Non-CR/non-PD’ is preferred over ‘stable disease’ for non-target disease since SD is increasingly used as an endpoint for assessment of efficacy in some trials so to assign this category when no lesions can be measured is not advised

#### 11.1.5 Duration of Response

Duration of overall response: The duration of overall response is measured from the time measurement criteria are met for CR or PR (whichever is first recorded) until the first date that recurrent or progressive disease is objectively documented (taking as reference for progressive disease the smallest measurements recorded since the treatment started).

The duration of overall CR is measured from the time measurement criteria are first met for CR until the first date that progressive disease is objectively documented.

Duration of stable disease: Stable disease is measured from the start of the treatment until the criteria for progression are met, taking as reference the smallest measurements recorded since the treatment started, including the baseline measurements.

#### Progression-Free Survival

PFS is defined as the duration of time from start of treatment to time of progression or death, whichever occurs first.

## 12.0 DATA REPORTING/PROTOCOL DEVIATIONS

---

### 12.1 Data Reporting

#### 12.1.1 Confidentiality and Storage of Records

Electronic data collection will be used for this protocol. The data will be stored in encrypted, password protected, secure computers that meet all HIPAA requirements. When results of this study are reported in medical journals or at meetings, identification of those taking part will not be disclosed. Medical records of participants will be securely maintained in the strictest confidence, according to current legal requirements. They will be made available for review, as required by the FDA, HHS, or other authorized

users such as the NCI, under the guidelines established by the Federal Privacy Act and rules for the protection of human participants.

#### 12.1.2 Data Collection Forms and Submission Schedule

All data will be collected using electronic data collection, stored as indicated in Section 12.1.1, and will be submitted according to the timelines indicated in Table 14.1.3.

#### 12.2 Table 12.1.3 Data Submission Schedule

Form	Submission Timeline
Eligibility Checklist	Complete prior to registration
On Study Forms	Within 14 calendar days of registration
Baseline Assessment Forms	Within 14 calendar days of registration
Treatment Forms	Within 14 calendar days of the last day of cycle
Adverse Event Report Forms	Within 14 calendar days of the last day of cycle
Response Assessment Forms	Within 14 calendar days of the last day of cycle
Other Assessment Forms (concomitant medications, chemistry, hematology, physical exam etc.)	Within 14 calendar days of the last day of cycle
Off Treatment/Off Study Forms	Within 14 calendar days of completing treatment or being taken off study for any reason
Follow up/Survival Forms	Within 30 calendar days of the protocol defined follow up visit date or call

#### 12.3 Protocol Deviations

##### 12.3.1 Deviation Policy

This protocol will be conducted in accordance with COH's "Clinical Research Protocol Deviation Policy" located at <http://www.coh.org/dsmc/Documents/Institutional%20Deviation%20Policy.pdf>.

Deviations from the written protocol that could increase participant risk or alter protocol integrity require prior IRB approval of a single subject exception (SSE) request. In addition, if contractually obligated, the sponsor must also approve the deviation. IRB pre-approved SSE protocol modifications are considered an amendment to the protocol and not a deviation. The submission of a deviation report is not required.

Brief interruptions and delays may occasionally be required due to travel delays, airport closure, inclement weather, family responsibilities, security alerts, government holidays, etc. This can also extend to complications of disease or unrelated medical illnesses not related to disease progression.

##### 12.3.2 Reporting of Deviations

All deviations will be reported to the COH DSMC within five days. The DSMC will forward the report to the IRB following review.

##### 12.3.3 Resolving Disputes

The COH Investigational Drug Service (IDS) cannot release a research agent that would cause a protocol deviation without approval by the PI. Whenever the protocol is ambiguous on a key point, the IDS should rely on the PI to clarify the issue.

In situations where there is misperception or dispute regarding a protocol deviation among the persons involved in implementing the protocol, it is the responsibility of the PI to resolve the dispute and the PI may consult with the DSMC chair (or designee) to arrive at resolution.

## **13.0 STATISTICAL CONSIDERATIONS**

---

### **13.1 Study Design**

The primary hypothesis is that the combination of FOLFIRI + panitumumab has activity in patients with *RAS/RAF* WT mCRC when introduced as a re-challenge to patients that had previous clinical benefit with anti-EGFR therapy (at least 6 months PFS or PR or CR by RECIST criteria), have subsequently received and progressed following a non-anti-EGFR containing regimen, and have not been exposed to anti-EGFR therapy for at least 4 months.

While previous work [12] demonstrated a response rate of 54% with cetuximab-rechallenge in this patient population, enrolled patients were highly selected, with a first-line cetuximab response rate of 90%. In addition, the first-line median PFS was 10 months (range 3-30), and the median PFS on re-challenge was 6.6 months with a range (~2 to ~20) and 95% CI (4.1-9.0 months). As we will not know a priori the response rate to first-line anti-EGFR therapy, nor the median PFS with previous anti-EGFR therapy, and this study will not be restricted to two prior chemotherapy regimens due to treatment patterns in the US, we can't use the cetuximab estimates for this trial. As a result, we will design this study according to:

1. If the response is clearly below 20%, the study will stop early, unless the PFS looks promising (defined below).
2. If the study does not stop early, we will enroll a total of 25 participants to better estimate the response rate, PFS, and compare the PFS to prior anti-EGFR therapy to the PFS (pairwise) on this re-challenge (similarly for responses).
3. Evaluate the role of biological correlatives.

As a result, we will employ a modification of the Gehan 2-stage Phase II design. In the first stage, 14 participants will be accrued. Failure to observe a response if the true response is 20% or above would occur with a probability less than 5% (4.4%). Failure to observe at least 4 participants progression-free at the second evaluation (~4 months), would occur with less than 3% probability if the true 4-month PFS rate is 50%, and would occur with more than 95% probability if the true 4-month PFS rate was 10%, which is higher than placebo treatment 4-month PFS seen on the CORRECT trial.[1] As a result, if no objective responses are observed in 14 participants, and fewer than 4 participants are progression-free at the 4 month evaluation, the study will close for futility. If there is at least one response, or at least 4 participants progression-free at 4 months, an additional 11 participants will be accrued. The interim stopping for futility is such that there is a 46% chance of early stopping if the response rate is 5% and the 4-month PFS rate is 10%. This compares to 48.7% early stopping probability for the standard Gehan design if the true response rate is 5%, but allows us to pass the interim stopping condition if PFS suggests enough activity due to re-challenge to expand to a total of 25 participants.

With a total of 25 participants, the standard error of estimate for the response rate estimate and the 4-month PFS rate estimate will not exceed 10%.

All of the participants who met the eligibility criteria (with the exception of those who received no study medication) will be included in the main analyses of response and PFS, and all the secondary or correlative analysis described below.

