##### Nature of Illness and Treatment History

- \_\_\_ 6. Histologically confirmed colon or rectal cancer with metastatic disease.
- \_\_\_ 7. Extended RAS and BRAF wild type status documented on archival tumor tissue or on fresh biopsy if no archival tissue present.
- \_\_\_ 8. Measurable disease defined by at least 1 lesion  $\geq 1$  cm.
- \_\_\_ 9. Documented objective response or stable disease lasting for 6 months or more to last prior anti-EGFR (cetuximab or panitumumab) in combination with irinotecan or FOLFIRI.
- \_\_\_ 10. Progression within 6 weeks following their last dose of anti-EGFR therapy.
- \_\_\_ 11. Treatment with a non-EGFR targeting regimen following progression on anti-EGFR plus irinotecan-based therapy.
- \_\_\_ 12. At least 4 months from prior anti-EGFR therapy prior to start of study treatment.
- \_\_\_ 13. At least three weeks from any non-anti-EGFR therapy prior to start of study treatment. Any number of prior therapies is permitted.
- \_\_\_ 14. Adequate recovery in the investigators opinion from any clinically significant toxicity from prior therapy.

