### **13.3 Statistical Analysis Plan**

Progression-free survival will be estimated using the product-limit method of Kaplan and Meier. As secondary endpoints, we will investigate the impact of PFS and response on prior anti-EGFR therapy and the time since last anti-EGFR exposure on the response rate and PFS on the current study.

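### The pairwise comparison with prior anti-EGFR therapy is tilted against re-challenge, because only the prior outcome was a condition of entry

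*Combined protocol and SAP*

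**What the plan says.** Section 13.1 lists three design purposes. The second, given as a reason for enrolling all 25 participants, includes a within-patient comparison: the trial will "compare the PFS to prior anti-EGFR therapy to the PFS (pairwise) on this re-challenge", and will treat response in the same way.

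Entry depends on the first half of that pair. Inclusion criterion 9 requires "Documented objective response or stable disease lasting for 6 months or more to last prior anti-EGFR" therapy, and the primary hypothesis in 13.1 repeats the filter as "at least 6 months PFS or PR or CR by RECIST criteria". Criterion 10 adds "Progression within 6 weeks following their last dose of anti-EGFR therapy", so every prior PFS ends in an observed event.

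The second half has no filter on its length. Under Progression-Free Survival in section 11, "PFS is defined as the duration of time from start of treatment to time of progression or death, whichever occurs first".

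Section 13.3 describes something different from a paired comparison: "we will investigate the impact of PFS and response on prior anti-EGFR therapy" and of time since last exposure on current response and PFS. That is an association, and it matches secondary objective 3. Section 13.3 gives no paired method, no reference value, no censoring rule for the pairs and no remark on selection.

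**The concern.** When patients are chosen because one of two measurements was good, the other will on average be less good, even if nothing has changed. Here the chosen measurement is the prior outcome, so the comparison leans against re-challenge unless the two outcomes in a patient are perfectly correlated. Response has the same problem, because a prior response is itself a route into the trial.

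The plan sees this kind of selection elsewhere. Section 13.1 says of the cited cetuximab re-challenge study that "enrolled patients were highly selected, with a first-line cetuximab response rate of 90" per cent, and for that reason (among others) declines to use its estimates for design. It does not apply the thought to its own paired comparison.

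The trial's rationale is that a break from anti-EGFR therapy restores sensitivity. A paired comparison with the earlier exposure is what readers would naturally take as the test of that. A re-challenge PFS shorter than prior PFS could be read as failed re-sensitisation when selection alone might explain it, and the plan gives readers no means of telling.

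**Working it through.** **The plan's own figures.** None is attached to the paired comparison. The neighbouring design figures in 13.1 reproduce by exact binomial:

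- P(0 of 14 | 0.20) = 0.80^14 = 0.044 (stated 4.4%)
- P(fewer than 4 of 14 | 0.50) = 0.029 (stated below 3%)
- P(fewer than 4 of 14 | 0.10) = 0.956 (stated above 95%)
- P(0 of 14 | 0.05) = 0.95^14 = 0.488 (stated 48.7%)
- Early stopping, taking response and PFS as independent: 0.4877 × 0.9559 = 0.466 (stated 46%)
- Standard error at n = 25: √(0.25/25) = 0.10 (stated at most 10%)

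None of these uses the prior outcome, so none is touched by this point.

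**Inputs for the paired comparison.** From the documents: the entry filter (criterion 9), and two medians used only to set a plausible range, 10 months first-line and 6.6 months on re-challenge in the cited study. Assumed, because the documents do not give them: lognormal PFS, log-SD 0.7 to 0.9, within-patient correlation 0 to 0.8, no censoring, and the same PFS distribution on both exposures, so that there is no true loss of efficacy.

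**A case that can be done by hand.** Let T1 be prior PFS and T2 re-challenge PFS, independent with common survival function S. Suppose entry requires T1 ≥ 6. Then P(T2 > T1 and T1 ≥ 6) = S(6)²/2, and dividing by S(6) gives

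P(T2 > T1 | T1 ≥ 6) = S(6)/2.

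- Median 6.6, log-SD 0.9: S(6) = 1 − Φ(ln(6/6.6)/0.9) = 1 − Φ(−0.106) = 0.542; share = 0.27.
- Median 10, log-SD 0.7: S(6) = 1 − Φ(ln(6/10)/0.7) = 1 − Φ(−0.730) = 0.767; share = 0.38.

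Without selection the share is 0.50.

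**The filter as written.** Criterion 9 also admits a prior responder whose PFS was under 6 months. How many such patients would enter is unknown, so the simulation (at least 1,000,000 pairs per setting, full range of medians, log-SDs and correlations) was run under several assumptions:

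| Prior PFS under 6 months admitted | Share of pairs favouring re-challenge | Median within-pair ratio T2/T1 |
|---|---|---|
| none | 27% to 45% | 0.53 to 0.95 |
| half of those at 4 to 6 months | 32% to 46% | 0.60 to 0.96 |
| half of those at 2 to 6 months | 39% to 48% | 0.71 to 0.97 |
| half of all those under 6 months | 42% to 48% | 0.78 to 0.98 |

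In each row the low end is at correlation 0 and the high end at 0.8.

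**A second model.** Weibull PFS (shape 1 or 1.5; unselected median 5, 7 or 10 months), nominal response rate 40% or 60%, latent response–PFS correlation 0.5, within-patient correlation 0 to 0.9, and the response-or-6-months filter applied explicitly. With equal activity:

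- P(T2 ≥ T1) is 0.29 to 0.47.
- The ratio of median PFS (re-challenge to prior) is 0.53 to 0.84 at correlation 0 and 0.97 to 1.00 at correlation 0.9.
- Response is 51% to 87% on prior therapy against 36% to 69% on re-challenge, a spurious gap of about 5 to 32 points.

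The response gap can be checked by hand. All prior responders are admitted, so the prior rate among enrolled patients is the unselected rate divided by the fraction admitted. At shape 1, median 5 months, the higher response rate and correlation 0, that is 0.52/0.61 = 0.85 (0.84 in the simulation; the difference is rounding), against 0.52 on re-challenge: a gap of 32 points with no true difference.

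**The case against.** The strongest reply is that little rests on this comparison. It is part of one sentence in a design list. The primary objective is to estimate response rate and PFS, futility uses only response and 4-month PFS, and 13.3 plans an association, which selection does not turn into a verdict on re-challenge. As a description of these selected patients the paired difference is not wrong; it misleads only when read as relative activity. All of that stands, and it limits the point to interpretation.

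The size is also open. Zero correlation is the unfavourable extreme, and it sits awkwardly with a design that picks prior beneficiaries because they are thought likely to benefit again. Criterion 10 leaves out patients still benefiting from prior therapy, which works somewhat the other way and was not simulated. This stands too.

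A reader might infer that the trial will probably declare re-challenge worse. With 25 uncensored pairs, a sign test calling re-challenge worse at 7 or fewer favourable pairs would do so with probability 64% at a 27% share. The documents do not support that figure as a property of the plan: they propose no sign test or any other paired test, and the 27% share requires every prior PFS to be at least 6 months, which criterion 9 does not.

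A reader might also infer that the comparator must be replaced by PFS on the last non-anti-EGFR regimen. That answers a different question and carries indirect selection of its own: criteria 10, 12 and 13 together tend to favour longer intervening treatment, and patients had to come through it fit for entry.

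What survives is the mechanism and its direction. Nothing in 13.1 or 13.3 warns the reader of either.

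**Conclusion.** The point holds as a matter of interpretation. Under equal efficacy, the paired PFS and response comparisons in 13.1 item 2 lean against re-challenge; every setting examined under both models did so. Under the lognormal assumptions, about 27% to 48% of pairs favour re-challenge instead of 50%, and the median ratio is 0.53 to 0.98 instead of 1. Where in that range the trial would fall depends on the within-patient correlation and on how many prior responders with PFS under 6 months enter. The documents give neither, and at high correlation the bias is small.

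This does not make the trial's main results unsound: the single-arm response and PFS estimates and the futility rule do not use the prior outcome. Nor does it show that the fall from 10 to 6.6 months in the cited study (ratio 0.66) was due to selection. A ratio of that size is within what selection alone could produce under these assumptions, but later-line disease or a real loss of activity could produce it too.

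**What to change.** In 13.1 item 2 and 13.3:

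1. Use prior PFS and prior response as covariates for re-challenge outcome, as secondary objective 3 intends, and bring item 2 into line with 13.3.
2. Report any paired PFS or response summary as descriptive only. State beside it that criterion 9 selects on the prior outcome, that the expected direction is against re-challenge, and that the summary is not evidence of reduced activity or failed re-sensitisation.
3. Report the PFS ratio by Kaplan-Meier, treating it as censored where the re-challenge time is censored, and give the number censored. Since the event and the censoring point are both divided by prior PFS, censoring on the ratio scale is not strictly independent; this is tolerable for a descriptive summary with few censored pairs.
4. Base the conclusion on activity on the single-arm response rate and PFS.

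Optionally, show a sensitivity range for the share and ratio expected under equal efficacy, with its assumptions stated. PFS on the last non-anti-EGFR regimen may be added as a supplementary descriptive comparator, noting that its progression dates come from routine care and not from a fixed scan schedule.

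Eligibility, treatment and sample size do not change. The cost is a few sentences of analysis-plan text, plus one more chart-derived date per patient if the supplementary comparator is used. The one real loss is that the paired comparison no longer stands as an efficacy result.
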